2.4 Statistical Framework

2.4.1 Hypothesis Test

The primary null hypothesis is that there is no difference between #Utviklingsklar and usual practice in the injury severity score in youth handball players over one season. There is only

STATISTICAL ANALYSIS PLAN for Effectiveness of the Injury-preventive Program #Utviklingsklar

one identified primary analysis. All other effectiveness analyses will be regarded as supportive.

2.4.2 Decision Rule

This trial is designed to address a single primary outcome. A group difference is claimed if the primary null hypothesis is rejected on the significance level (alpha) of 0.05 (two-sided).

2.5 Statistical Interim Analyses and Stopping Guidance

There will be no interim analysis in this trial. Due to the projects' assumed low risk of harm or unforeseen events for participants, along with a short project duration and data collection period, the establishment of an independent data monitoring committee is not deemed necessary. There is also no perceived necessity for routine collection and evaluation of adverse events.

2.6 Timing of Outcome Assessments

All planned measures and data collection are scheduled according to figure 1. Besides the baseline data collection, questionnaires are kept open for submission for two weeks (players) and three weeks (coaches) at each data collection timepoint. These periods are referred to as outcome assessment windows.

Activities	Participant	-1	0	T1	T2	T3
		Pre study Recruitment and consent	Pre study Baseline	Study Pre-season	Study In-season	Study Post-season
Recruitment and consent	Players, parents, coaches, club leaders	x				
Randomization	Club		x			
Quantitative data collection						
Demographics questionnaire	Players, coaches, club leaders		x			
Injury surveillance*	Players				x	
Behavior questionnaire	Coaches		x		x	x
Injury-preventive coaching practices	Coaches		x			x

*Conducted with biweekly measurements through the season

Figure 1. Timeline of outcome assessments of #Utviklingsklar.

- Pre-study baseline coaches: 13.05.2024.-29.08.2024
- Pre-study baseline players: 26.08.2024- 17.11.2024
- Study in season coaches: 06.02.2025-02.03.2025
- Study in season players: week 42, 44, 46, 48, 50, 52 of 2024 and 2, 4, 6, 8, 10, 12, 14 of 2025. Players pilot tested their questionnaire during the recruitment phase, these data are not included in the data collection time periods.
- Study post-season coaches: 21.04.2025-07.05.2025

2.7 Timing of Final Analysis

The main analysis is planned when all clubs have been given the opportunity to attend/conduct all parts of the intervention, data at the post-season assessments have been entered, verified and validated and the primary database has been locked.

3. Statistical Principles

STATISTICAL ANALYSIS PLAN for Effectiveness of the Injury-preventive Program #Utviklingsklar

3.1 Confidence Intervals and p-values

All calculated p-values will be two-sided and compared to a 5% significance level. If a p-value is less than 0.05, the corresponding group difference will be denoted as statistically significant. All effectiveness estimates will be presented with two-sided 95% confidence intervals. As there is only one primary hypothesis to be tested in this trial, there will be no adjustments for multiplicity.

3.2 Adherence and Protocol Deviations

Adherence to the intervention will be based on the description of fidelity and dose of #Utviklingsklar's three main components: 1) the e-learning, 2) the workshop, 3) the mid-season meeting. No cut-off for adherence will be defined.

3.3 Analysis Populations

The Enrolled Set will include all participants who have provided informed consent and have been included in the study database. The Full Analysis Set (FAS) will be defined as all participants randomly assigned to the groups having responded to the OSTRC questionnaire on health problems at least once (see Sections 2.6 and 5.1.1.4).

4. Trial Population

4.1 Screening Data, Eligibility and Recruitment

Clubs will be eligible for participation if they are able to participate with one club leader, 2-6 teams (teams from at least two different age groups (13-17) and both the boy and girl league should ideally be represented), and a minimum of one coach from each of the participating teams.

A CONSORT flow diagram (18) will be used to summarize the number of participants who were:

- Included and randomised
- Received the intervention
- Lost to follow-up (reasons will be provided)
- Randomised and included in the primary analysis

4.2 Withdrawal/Follow-up

The status of included and randomised participants will be tabulated by group according to:

- Completed intervention and assessments
- Completed assessments but not intervention
- Withdrew consent
- Lost to follow-up

Timing of withdrawal will be presented with numbers and reasons for withdrawal (and exclusion from analysis) given at each stage.

4.3 Baseline Participant Characteristics

STATISTICAL ANALYSIS PLAN for Effectiveness of the Injury-preventive Program #Utviklingsklar

The baseline participant characteristics to be summarized include:

Players	Age, gender, player position (handball), previous injury, player experience (years), participation in other sports and weekly hours of participation in other sports.
Coaches	Age, gender, education in health-related field, education within injury diagnosis/treatment/prevention, university-level coaching education, completed coaching courses, satisfaction with injury prevention knowledge in coaching courses, coaching experience (years), receiving salary for coaching, employed by club in full-time position, possessing multiple club roles.
Clubs	Club member fee (kroner), club provides coach salary, club employs full time coaches, number of fulltime coaches, club employs fulltime leaders, number of fulltime leaders, the club possesses an injury preventive plan, club teams' participation in Skadefri club event within previous two years.

Demographics and baseline characteristics will be summarized by randomised group using descriptive statistics (N, mean, standard deviation, median, 25/75 percentiles) for continuous variables, and number and percentages of participants for categorical variables.

5. Analysis

5.1 Outcome Definitions

All definitions and variables for players are based on the IOC consensus statement on methods for recording and reporting of epidemiological data on injury and illness in sport (19) and its adaptation to team ball sports (20). Definitions and variables for coaches behavioral determinants builds on the Health Action Process Approach (HAPA-model) (21).

5.1.1 General Definitions and Derived Variables

5.1.1.1 *Health problems*

A *health problem* is defined as any condition that reduces an athlete's normal state of full health, irrespective of its consequences on the athlete's sports participation or performance or whether the athlete sought medical attention. This constitutes an umbrella term that includes, but is not limited to, injury and illness. A health problem is further divided into injury and illness. *Injury* is defined as tissue damage or other derangement of normal physical function due to participation in sports, resulting from rapid or repetitive transfer of kinetic energy. *Illness* is defined as a complaint or disorder experienced by an athlete, not related to injury. Illnesses include health-related problems in physical, mental or social well-being, or removal or loss of vital elements.

5.1.1.2 *Exposure*

Exposure is defined as the time during which athletes are at risk of injury and is recorded for each individual within a team. *Training exposure* is quantified as the weekly hours of training during the observation period. *Match exposure* is quantified as the weekly minutes of match play during the observation period.

5.1.1.3 *Match season*

STATISTICAL ANALYSIS PLAN for Effectiveness of the Injury-preventive Program #Utviklingsklar

The match season is defined as the week the most teams start their regular league season and the week where this season ends.

5.1.1.4 The Oslo Sports Trauma Research Center Questionnaire on Health Problems

The Oslo Sports Trauma Research Center Questionnaire on Health Problems (OSTRC-H2) is used to collect all player data. It consists of four key questions about health problems impact on 1) participation in sports, 2) training volume, 3) performance, and 4) symptoms of health problems during the past 7 days. It also contains additional questions on injury and exposure. The questionnaire is self-reported by players and is administrated biweekly throughout the match season.

5.1.2 Primary Outcome Definition

The primary outcome is the weekly injury severity score during the match season. The injury severity score is derived from responses to each of the four OSTRC-H2 questions, measured at 13 time points during the match season (see Section 2.6). Each question is assigned a score ranging from 0 to 25, culminating in a total injury severity score from 0 to 100 at each time point. If a player reports more than one injury at a given data collection timepoint, the injury severity score will be calculated as the maximum of the reported injury severity scores.

5.1.3 Secondary Outcomes Definitions

5.1.3.1 Injury consequence outcomes

1. The weekly injury severity score during the match season for sudden and gradual onset injuries.
2. The weekly injury severity score during the match season for lower leg, ankle/foot, knee and shoulder injuries.
3. The weekly injury severity score during the match season for sudden onset lower leg, ankle/foot, knee and shoulder injuries.
4. The weekly injury severity score during the match season for gradual-onset lower leg, ankle/foot, knee and shoulder injuries.
5. Injury burden, defined as the sum of injury severity score divided by the sum of exposure (per 1000 hours), where the sums are over team and over match season. The unit of analysis for burden is thus team and not player. Only pairs of severity score and exposure for each player will be counted (i.e. if a player has missing data for either the severity score or the exposure at a time point, neither will be counted for that timepoint).

5.1.3.2 Behavioral determinant outcomes

Behavioral determinant outcomes are defined as the coaches change in aggregated behavioral determinant scores from baseline to mid-season and from baseline to end-of season.

The aggregated scores include the determinants 1) risk perception, 2) intention, 3) outcome expectancies, 4) action self-efficacy, 5) maintenance self-efficacy, 6) coping self-efficacy, 7) recovery self-efficacy, 8) action plans 9) coping plans and 8) club social support at baseline, mid-season and at end of season. Behavioral determinants will be measured with the *Sports*

STATISTICAL ANALYSIS PLAN for Effectiveness of the Injury-preventive Program #Utviklingsklar

Injury Preventive Behavior Questionnaire containing 56 items with three to six items within each determinant, all assessed using a 7-point Likert scale. The 7-point Likert responses will be transformed into aggregate scores by summing the items related to each determinant and dividing this total by the maximum possible score, resulting in values ranging from 0.14 to 1.0.

5.1.3.4 Injury-preventive coaching practices outcomes

The injury-preventive coaching practice outcomes consist of:

1. The change in the extent to which teams complete warm-up as described in the intervention from baseline to end-of season.
2. The change in the extent to which teams complete strength training as described in the intervention from baseline to end-of season.
3. The change in the extent to which players with pain or injuries receive guidance on medical care from baseline to end-of season.
4. The change in the extent to which training and match participation is facilitated for players with pain or injuries from baseline to end-of season.

Coaches will report injury-preventive coaching practices in a study-specific 7-point Likert scale questionnaire at baseline and at end of season. The endpoint will be the change measured on a 7-point scale, which is then converted into a 13-point scale ranging from -6 to +6.

5.1.4 Overview of Outcomes

Level	Outcome	Timeframe	Type
Primary	Weekly injury severity score	Baseline to end-of season (measured biweekly)	Continuous
	Weekly injury severity score for sudden and gradual onset injuries.		
	Weekly injury severity score for lower leg, ankle/foot, knee and shoulder injuries.		
	Weekly injury severity score for gradual-onset lower leg, ankle/foot, knee and shoulder injuries.		
	Weekly injury severity score for sudden onset lower leg, ankle/foot, knee and shoulder injuries		
	Injury burden		
Secondary	Change in aggregated behavioral determinant scores	Baseline to mid-season and baseline to end of season	Continuous
	Extent to which teams complete warm-up as described in the intervention	Baseline to end-of season	Ordinal
	Extent to which teams complete strength training as described in the intervention.		
	Extent to which players with pain or injuries receive guidance on medical care.		
	Extent to which training and match participation is facilitated for players with pain or injuries.		

5.2 Analysis Methods

STATISTICAL ANALYSIS PLAN for Effectiveness of the Injury-preventive Program #Utviklingsklar

All statistical analyses will be performed on the full analysis set (FAS).

5.2.1 Primary Outcome

Analysis

The primary outcome (weekly injury severity score) will be analyzed with a linear mixed model. The model will include fixed effects for intervention (intervention vs control), time point, intervention x time point interaction, and geographical region (stratification factor in the randomisation). Time point is defined as 1 for the first response to the OSTRC questionnaire (week 42, 2024), 2 for the second response to the questionnaire (week 44, 2024), and so on until 13 for the last response (week 14, 2025). The model will include random intercepts for players nested within clubs. The predicted margins over all time points will be presented for intervention and control separately with 95% confidence intervals (CIs). The effect measure will be the difference between the weekly injury severity score for intervention and control, estimated as the predicted marginal effect of intervention over all time points, based on the fitted linear mixed model. The effect estimate will be presented with a 95% CI and a P-value for the null hypothesis of a difference equal to zero.

The predicted margins for intervention and control will be presented with 95% CIs for each time point in a plot. The estimated intervention effect (difference between intervention and control) with a 95% CI for each time point will also be shown in a plot.

Assumption checks

The distribution of the primary outcome (injury severity score) will be assessed with descriptive statistics and histograms. With a sample size of approximately 2000, the linear mixed model will be robust to quite large deviations from the normal distribution, and the injury severity score is bounded below at 0 and above at 100, so its distribution cannot be severely skewed. Still, in the unlikely case that the distribution of the outcome is deemed to deviate too much from the normal distribution, a log transformation of the outcome will be done prior to fitting the linear mixed model. In that case, an analysis of the untransformed data will be performed as an additional sensitivity analysis. After fitting the model (original scale or log transformed), plots of observed and model-fitted values (by intervention group and time point) will be compared to assess the fit of the model.

Missing data

The linear mixed model will handle missing data in one or more time points per player under the assumption of missing at random. No patient in the FAS has missing data on all fourteen time points, per the definition of FAS (see section 3.3).

Subgroup analysis

A subgroup analysis of the primary outcome will be performed by team gender. The analysis will be as described for the primary analysis of the primary outcome above; however, instead of an interaction term between intervention and time point, there will be a three-way interaction between intervention, time point, and team gender. The results will be a separate estimated intervention effect across all time points for each team gender and separate plots of estimated intervention effects for each time point for each team gender. No hypothesis tests for intervention effects will be performed.

STATISTICAL ANALYSIS PLAN for Effectiveness of the Injury-preventive Program #Utviklingsklar

A test for subgroup effect (i.e. a test for the null hypothesis of equal intervention effects for each team gender) will be calculated with a likelihood ratio test for the models with and without interaction by team gender.

Sensitivity analyses

The following sensitivity analyses will be performed for the primary outcome:

- Analysis restricted to the first part of the season (2024, time point 1-6)
- Analysis restricted to the second part of the season (2025, time point 7-14)
- Analysis on untransformed data (only if the primary analysis is done on log-transformed data)

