2.2 Randomisation

Upon enrolment, clubs will be randomly assigned to either the control or intervention group in a 1:1 allocation ratio, using a computer-generated cluster randomisation schedule, taking differences in cluster size into account and stratified by geographical region. The biostatistician responsible for the randomisation and primary statistical analysis will be blinded to group allocation. It is impossible to blind players, coaches, and clubs to group allocation. For practical reasons (i.e., data monitoring and participant follow-up), neither the PhD students nor the principal investigator will be blinded.

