5.2.5 Ordinal Secondary Outcomes

Analysis

STATISTICAL ANALYSIS PLAN for Effectiveness of the Injury-preventive Program #Utviklingsklar

The ordinal secondary outcomes on coach practices are measured as the change in an ordinal 7-point scale from baseline to end of season. The change (baseline minus end of season) will be an outcome ranging from -6 (score 1 at baseline and 7 at end of season) to 6 (score 7 at baseline and 1 at end of season). This outcome is an ordinal outcome with 13 categories. With approximately 120 coaches, many of the categories will be sparsely populated, and we believe that an ordinal regression model would be a poor choice with these many categories and so few data. Instead, we will compare the mean number of categories of change from baseline to end of season for intervention vs. control. The outcomes will be analyzed with linear regression models with intervention (intervention vs control) and geographical region (stratification factor in the randomisation) as the explanatory variables. The standard errors will be adjusted to account for clustering within clubs. Based on the fitted model, the predicted margins for intervention and control separately and the predicted marginal effect of intervention will be presented with 95% CIs. The observed counts (and percentages) on the original 13-point ordinal scale will be presented for intervention and control.

Assumption checks

The distributions of the residuals from the fitted linear regression models will be assessed with descriptive statistics and histograms. With only 13 possible outcomes, it is very unlikely that the distribution of the residuals will exhibit any signs of large deviations from the normal distributions. Still, in the case that the distribution of the outcome is deemed to deviate too much from the normal distribution, a log transformation of the outcome will be done prior to fitting the model.

Missing data

The main analysis of the ordinal secondary outcomes will be performed on the complete case sample. As a sensitivity analysis, we will impute missing data with multiple imputation. The imputation model will be multinomial logistic regression, stratified by intervention/control, and it will include the following explanatory variables:

- Age level (team)
- Sex (team)
- Education in injury diagnosis/treatment/prevention (coach)
- Access to health personnel (team)
- Coaching experience (coach)
- University-level coaching education (coach)

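### The primary model adjusts only for region; adding team gender and team age level is a cheap, optional improvement to a valid analysis, with a gain between about zero and 7 points of power.

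*SAP*

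**What the plan says.** Section 5.2.1 has the same model structure in both SAPs. Beyond the main terms for arm and time, the fixed effects are given as "intervention x time point interaction, and geographical region (stratification factor in the randomisation". On the random part it says: "The model will include random intercepts for players nested within clubs". No other baseline variable enters.

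Under section 2.2, clubs are "randomly assigned to either the control or intervention group in a 1:1 allocation ratio", and the schedule is described as "taking differences in cluster size into account and stratified by geographical region". Nothing in the randomisation balances the gender or age mix of clubs.

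Section 4.1 admits clubs with "2-6 teams (teams from at least two different age groups (13-17) and both the boy and girl league should ideally be represented". The spread over leagues is a preference, so a club's composition can vary.

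Both variables are already planned for other uses. Team gender defines the subgroup analysis of the primary outcome in 5.2.1. Team sex and "Age level (team") are predictors in the imputation model of 5.2.5. Player age and gender are baseline items in 4.3.

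**The concern.** In a trial with 26 to 30 clubs, the standard error of the primary effect is driven mainly by differences between clubs. If injury severity differs by gender or age, and clubs differ in their mix of the two, part of the between-club variance comes from composition and could be removed by adjustment. Region-only adjustment leaves it in the error term.

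The mix could also be uneven between arms in two ways:

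- **By chance.** Only region and cluster size are controlled in the allocation.
- **Through response.** The full analysis set keeps only players who answered the injury questionnaire at least once (3.3), and players, coaches and clubs know their allocation (2.2). If response depends on age or gender differently in the two arms, the analysed mix shifts after randomisation. The model also assumes data missing at random given what it contains, which is more plausible with these two variables included.

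Both are team attributes that the intervention cannot change, and in a linear model adjusting for them leaves the mean-difference estimand as it is.

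**Working it through.** **Inputs (section 2.3, same in both SAPs).** Difference 34 − 25.5 = 8.5; SD 30; ICC 0.05; 64 players per club; two-sided alpha 0.05; 80% power; 13 clubs per arm needed, 15 targeted. Which arm carries which mean does not affect the difference.

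**Reproducing the plan's figure.**
- Individually randomised: n = 2 × [30 × (1.96 + 0.84)/8.5]² ≈ 196 per arm.
- Design effect: 1 + 63 × 0.05 = 4.15.
- 196 × 4.15 = 813.4 players; 813.4/64 = 12.71, rounded up to 13 clubs per arm.
- Normal-approximation power at 13 clubs: 81.0%.

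The stated size is confirmed and assumes no covariate gain.

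**Where the variance lies.** Between-club variance is 0.05 × 900 = 45. Within-club variance is 0.95 × 900 = 855, which contributes 855/64 = 13.4 to a club mean. The club-mean variance is 45 + 13.4 = 58.4, of which 45/58.4 = 77% is between clubs. Only differences in mix between clubs can matter much.

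**Effect of adjustment.** Let Rb and Rw be the shares of between-club and within-club variance that the covariates explain. For k clubs per arm:

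SE = √{2 × [45(1 − Rb) + 855(1 − Rw)/64]/k}

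Power comes from the noncentral t with noncentrality 8.5/SE and 2k − 2 degrees of freedom, or 2k − 4 if the two terms each use one at club level. The degrees of freedom used by region are ignored throughout, because the number of strata is not given. **Every Rb and Rw is an assumption; the documents give none.**

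| Rb / Rw | SE, k = 13 | Power, 24 df | Power, 22 df | Power, k = 15, 28 df |
|---|---|---|---|---|
| unadjusted | 3.00 | 77.7% | – | 83.7% |
| 0% / 0% (terms useless) | 3.00 | – | 77.4% | – |
| 0% / 5% | 2.98 | 78.2% | 77.8% | 84.1% |
| 5% / 2% | 2.93 | 79.5% | 79.1% | 85.2% |
| 10% / 2% | 2.87 | 81.1% | 80.8% | 86.6% |
| 20% / 5% | 2.74 | 84.6% | 84.3% | 89.6% |

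**Size of chance imbalance, gender alone.** Assume a boy–girl difference D of 2 to 6 points and a between-club SD s of the girls' share of 0.15 to 0.35. The SD of the resulting shift in the effect estimate is D × s × √(2/13): from 2 × 0.15 × 0.392 = 0.12 to 6 × 0.35 × 0.392 = 0.82 points, against a target difference of 8.5.

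**Why previous injury is different.** Player baseline ran to 17.11.2024 in handball, while outcome collection began in week 42 of 2024. In football it ran to 08.05.2025, while outcome collection began in week 17 of 2025 (section 2.6). A reported previous injury may therefore postdate the start of outcome collection. Team gender and age level do not have this problem.

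**The case against.** The strongest reply is that nothing here is wrong. The model adjusts for the randomisation stratification factor, the estimate is unbiased over randomisation, chance imbalance between clubs is part of what the standard error covers, and the sample size holds without any covariate gain. All of this stands.

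A reader might go further than the documents allow in four ways:

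- **That precision is lost.** This needs gender or age to predict severity and the mix to differ materially between clubs. The SAPs document neither. The eligibility wording that leaves the mix open, "both the boy and girl league should ideally be represented", also steers clubs towards a similar mix.
- **That imbalance is likely to be serious.** It is possible, but under the assumptions above the resulting shift is small against 8.5 points.
- **That adjustment rescues an underpowered trial.** The 77.7% applies at 13 clubs per arm, after all four spare clubs are lost. At the target of 15 it is 83.7% without covariates.
- **That adjustment is free.** If the terms explain nothing and use two club-level degrees of freedom, power drops by about 0.3 points.

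Two further replies stand in part. The gender subgroup model already gives gender-specific effects, but these are supportive and do not change the primary estimate; age level enters no player-outcome analysis. The SAPs also do not state that team age level is complete for every team. That is an inference from its planned use and from eligibility by age group, plausible but to be confirmed.

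**Conclusion.** The point holds as an optional improvement, not as an error or contradiction. Region-only adjustment is a sound prespecified analysis. Adding team gender and team age level uses data already planned, may improve precision, and gives some protection against an uneven mix from chance or response.

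At 13 clubs per arm the change in t-based power runs from about −0.3 points (77.7% to 77.4%) to about +7 (77.7% to 84.6%). It is below 2 points in the two weakest adjusted scenarios. These figures rest on the plan's SD, ICC and club size and on assumed explained-variance shares. If the covariates are weakly prognostic, or clubs have similar mixes, the gain is near zero.

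**What to change.** In 5.2.1 of both SAPs, add team gender and team age level as fixed effects in the primary model, and state how age level is coded. Carry the same terms to the severity-score outcomes in 5.2.2. Keep the region-only model as a named sensitivity analysis. Do not add previous injury, because player baseline collection overlaps the outcome weeks.

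Make the change before database lock or unblinding, since an adjustment added later would look data-driven. The SAPs give no lock date, so this timing must be checked.

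The cost is a sentence or two in each SAP, a check that both variables are complete for every team, and one or two club-level degrees of freedom (more if age level is entered in several categories). No new data should be needed if both variables prove complete.
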